1. VERSION HISTORY

This statistical analysis plan (SAP) for Study C3671001 is based on the protocol (Amendment 2) dated 11 Jun 2019.

Table 1. Summary of Major Changes in SAP Amendments

Version/ Date	Associated Protocol Amendment	Rationale	Specific Changes
1/ 31 Jul 2018	Amendment 1 (05 Jun 2018)	Not Applicable	Not Applicable
2/ 10 Oct 2019	Amendment 2 (11 Jun 2019)	Update according to protocol amendment 2	
• CCI [REDACTED]• CCI [REDACTED]• CCI [REDACTED]• CCI [REDACTED]• CCI [REDACTED]• CCI [REDACTED] 
E 4 has also been updated after the approval of protocol amendment 2. Renamed the evaluable immunogenicity populations.

Table 1. Summary of Major Changes in SAP Amendments

Version/ Date	Associated Protocol Amendment	Rationale	Specific Changes
3/ 11 Jun 2020	Amendment 2 (11 Jun 2019)	CCI [REDACTED]	
 • Used the appropriate SAP 2015 template, which does not include estimands. • Clarified the analysis cohorts, and defined the analysis population for each cohort. • CCI [REDACTED] • CCI [REDACTED] • Streamlined the structure on endpoints and analyses to follow the SAP template requirements. • Added local reactions and systemic events figures; added immunogenicity LLOQs for all assays. • Added the details of randomized subjects, vaccination visits, blood sample collections, and collections of e-diary data in each cohort. • Restructured and added the details of analyses for RSV A and RSV B neutralizing titer (NT), hemagglutination inhibition assay (HAI) CCI [REDACTED] • Edited the wording for the General Methods section; restructured the Assessing Interference section into Section 5.2.2. • Added immunogenicity analyses for the sentinel and expanded cohorts, CCI [REDACTED]

[REDACTED]

[REDACTED]

2. INTRODUCTION

This SAP provides the detailed methodology for summary and statistical analyses of the data collected in Study C3671001. A brief description of the study design and the study objectives is given below. Subsequent sections describe analysis populations and give the definitions of the safety and immunogenicity endpoints followed by details of statistical reporting. A list of tables, listings, and figures, mock-up tables, listings, and figures, and programming rules are prepared separately based on the methods described in this document. This document may modify the plans outlined in the protocol; however, any major modifications of the primary endpoint definition or its analysis will also be reflected in a protocol amendment.

2.1. Study Objectives

2.1.1. Primary Objective

- To describe the safety and tolerability of a respiratory syncytial virus (RSV) vaccine given alone or concomitantly with seasonal inactivated influenza vaccine (SIIV).

2.1.2. Secondary Objectives

- Sentinel and expanded cohorts: To describe the immune responses elicited by an RSV vaccine alone (sentinel and expanded cohorts) or with SIIV (expanded cohort only).
- Expanded cohort: To describe the immune responses elicited by SIIV alone or with an RSV vaccine.

CCI [REDACTED]

[REDACTED]

CCI [REDACTED]

[REDACTED]

[REDACTED]

[REDACTED]

CCI [REDACTED]

[REDACTED]

[REDACTED]

[REDACTED]

[REDACTED]

2.2. Study Design

This is a Phase 1/2, randomized, placebo-controlled, observer-blind, dose-finding first-in-human (FIH) study.

The study will evaluate the safety, tolerability, and immunogenicity of up to 6 RSV vaccine candidates with CCI [REDACTED] at 3 escalating dose levels of 60 µg CC [REDACTED] 120 µg CC [REDACTED] and 240 µg CCI [REDACTED] of the prefusion RSV F antigen, with or without aluminum hydroxide (Al[OH]₃), when administered alone or concomitantly with SIIV.

This study will utilize a sentinel cohort (Phase 1) and an expanded cohort (Phase 2) for each dose level in each age group. The age groups will run in parallel but independently from each other.

In the sentinel cohort (Phase 1), subjects will be enrolled into 2 age groups with equal numbers of subjects:

- Male and female subjects 18 to 49 years of age.
- Male and female subjects 50 to 85 years of age.

In the expanded cohort (Phase 2), subjects will be enrolled into 2 age groups with equal numbers of subjects:

- Male and female subjects 18 to 49 years of age.
- Male and female subjects 65 to 85 years of age.

In the sentinel cohort, approximate 168 subjects will receive a single intramuscular dose of the RSV vaccine candidate with or without Al(OH)₃ or placebo at Vaccination 1. Central randomization will take place in a 3:3:1 ratio for each dose level, by age stratum.

In the expanded cohort, 1014 subjects will be randomized equally across all dose/formulation levels, with or without SIIV, by age group via center-based randomization. This will include a total of 13 groups with an equal randomization ratio. Subjects in this cohort will receive 2 intramuscular injections at Visit 1 (Vaccination 1) and 1 intramuscular injection at Visit 2 (Vaccination 2). CCI [REDACTED]

CCI
[Redacted]

For both sentinel-cohort and expanded-cohort subjects, key safety data include electronic diary (e-diary) reports of local reactions and systemic events that occur within 14 days after Vaccination 1 (RSV vaccine or placebo). Adverse events (AEs) are collected from informed consent until 1 month after Vaccination 1 (Visit 3 for the sentinel cohort); and from consent until 1 month after Vaccination 2 (Visit 3 for the expanded cohort). AEs occurring up to 48 hours after blood draws are also collected. Medically attended AEs (MAEs) are collected after the AE collection period. Serious adverse events (SAEs) are being collected for all subjects from informed consent through 12 months after Vaccination 1.

CCI
[Redacted]

Blood samples are collected from all subjects for antibody testing. For sentinel-cohort subjects, blood samples are collected before Vaccination 1 and 2 weeks and 1, 2, 3, 6, and 12 months after Vaccination 1. For expanded-cohort subjects, blood samples for antibody testing are collected before Vaccination 1 and 1, 2, 3, 6, and 12 months after Vaccination 1.

CCI
[Redacted]

3. ENDPOINTS AND BASELINE VARIABLES: DEFINITIONS AND CONVENTIONS

3.1. Primary Endpoint(s)

Sentinel and Expanded Cohorts:

- Local reactions within 14 days after Vaccination 1.
- Systemic events within 14 days after Vaccination 1.
- AEs within 1 month after Vaccination 1.
- MAEs and SAEs through 12 months after Vaccination 1.

[Redacted]

[Redacted]

Expanded Cohort:

- AEs within 1 month after Vaccination 2.

3.1.1. Local Reactions

The local reactions reported in the e-diary are redness, swelling, and pain at the injection site, from Day 1 through Day 14 after vaccination, where Day 1 is the day of vaccination with RSV vaccine or placebo (Visit 1 for the sentinel/expanded cohort: [REDACTED])

This section describes derivations with details for the assessment of local reactions: any presence, maximum severity, duration, and onset day of local reactions, in addition to presence of severe local reactions on each day.

3.1.1.1. Presence of Local Reactions

For the summary of the presence (yes or no) of a local reaction during the interval from Day 1 through Day 14 after Vaccination 1 [REDACTED] where Day 1 is the day of vaccination, the following 2 variables are required in order to compute the proportions:

1. Presence (yes or no) of each local reaction on any day (Day 1 through Day 14).

The derivation is described in Table 2.

Table 2. Derived Variables for Each Local Reaction

Variable ^a	Yes (1)	No (0)	Missing (.)
Any day (Days 1-14)	Subject reports the reaction as “yes” on any day (Days 1-14).	Subject reports the reaction as “no” on all 14 days or as a combination of “no” and “missing” on all 14 days.	Subject reports the reaction as “missing” on all 14 days.

a. The variable will be defined for each of the 3 local reactions.

2. Presence (yes or no) of any local reaction on any day (Day 1 through Day 14);

For any local reaction on any day, a similar definition can be applied as given in Table 3.

Table 3. Derived Variables for Any Local Reaction

Variable	Yes (1)	No (0)	Missing (.)
Any day (Days 1-14)	Subject reports any local reaction as “yes” on any day (Days 1-14).	Subject reports the reaction as “no” on all 14 days or as a combination of “no” and “missing” on all 14 days for all 3 local reactions.	Subject reports all local reactions as “missing” on all 14 days.

3.1.1.2. Maximum Severity of Local Reactions

The grading of local reactions is listed in Table 4.

Table 4. Grading Scale for Local Reactions

	Mild Grade 1	Moderate Grade 2	Severe Grade 3	Grade 4^a
Redness	2.5 cm to 5.0 cm (5 to 10 measuring device units)	>5.0 cm to 10.0 cm (11 to 20 measuring device units)	>10 cm (>20 measuring device units)	Necrosis or exfoliative dermatitis
Swelling	2.5 cm to 5.0 cm (5 to 10 measuring device units)	>5.0 cm to 10.0 cm (11 to 20 measuring device units)	>10 cm (>20 measuring device units)	Necrosis
Pain (at the injection site)	Does not interfere with activity	Interferes with activity	Prevents daily activity	Emergency room visit or hospitalization for severe pain at the injection site

- a. Grade 4 assessment should be made by the investigator using the AE severity grading scale. The assessment will be collected on the AE case report form and thus not reported from the e-diary.

The following 2 variables are required in order to compute the proportions of subjects reporting maximum severity.

1. Maximum severity of each local reaction on any day (Day 1 through Day 14).

The maximum severity (highest grading) of each local reaction within 14 days after vaccination will be derived. The maximum severity will be derived as follows:

- = “Missing,” if values are missing for all days (Days 1-14);
- = 0, if the subject reports all reactions as “no” or a combination of “missing” and “no” for all days (Days 1-14);
- = Highest grade (maximum severity) within 14 days after vaccination, if the answer is not “no” for at least 1 day.

2. Maximum severity of any local reaction on any day (Day 1 through Day 14).

The maximum severity for any local reaction will be derived as follows:

- = “Missing,” if values are missing for all days (Days 1-14) across all 3 local reactions;
- = 0, if the subject reports all reactions as “no” or a combination of “missing” and “no” for all days (Days 1-14) for any individual local reaction;
- = Highest grade (maximum severity) within 14 days after vaccination, if the answer is not “no” for at least 1 day for at least 1 local reaction.

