3.1.1.5. Presence of Severe Local Reaction on Each Day

Presence (yes or no) of any severe local reaction on each of the 14 days (Day 1 through Day 14) follows the derivation as describe in Table 5.

Table 5. Derived Variables for Any Severe Local Reaction on Each Day

Variable	Yes (1)	No (0)	Missing (.)
Any severe local reaction on a specific day	Subject reports the severe reaction as “yes” on a specific day for any of the 3 local reactions.	Subject reports local reactions as any of the following: “no,” “mild,” or “moderate” (for 1-3 of the reactions) or missing (for 1-2 of the reactions) on that specific day.	Subject reports all 3 local reactions as “missing” on that specific day.

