6.1. Primary Endpoints

6.1.1. Local Reactions

6.1.1.1. Primary Analysis

Endpoint: Proportions of subjects reporting prompted local reaction within 14 days after vaccination.

- Analysis time points: Within 14 days after Vaccination 1.
- Analysis population: Safety population (sentinel cohort, expanded cohort, and combined sentinel and expanded cohorts).
- Analysis methodology: Descriptive summary statistics.
- Supporting objective: Primary objective.

Reporting Results:

Proportions of subjects reporting each and any local reactions after Vaccination 1 will be summarized by maximum severity level. Confirmed e-diary errors will be excluded from the analysis.

For each cohort, the percentage (%), the numerator (n) and denominator (N) used in the percentage calculation, and the corresponding 95% Clopper-Pearson CI will be presented for each vaccine group, by age stratum.

Figures: Bar charts with the proportions of subjects for each local reaction will be plotted for each vaccine group, by age stratum. The bar charts will be divided into severity subgroups to highlight the proportions of subjects by severity.

6.1.1.2. Additional Summary for Assessing Local Reactions After Vaccination 1

To support the assessment of local reactions, additional endpoints (as defined in Section 3.1.1) will be summarized. Confirmed e-diary errors will be excluded from these analyses.

Binary Endpoints

For each cohort, the percentage (%), the numerator (n) and denominator (N) used in the percentage calculation, and the corresponding 95% Clopper-Pearson CI will be presented for each vaccine group by age stratum for the following endpoints:

- Subjects reporting any severe local reaction on each day and any day (Day 1 through Day 14).

Continuous Endpoints

For each cohort, the following endpoints will be summarized by displaying n, mean, median, standard deviation, minimum, and maximum for each vaccine group, by age stratum:

- Duration of each systemic event after vaccination.
- Onset day of each systemic event after vaccination.
- Onset day of any systemic event after vaccination.

CCI

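### SAP Section 3.1.1.2 scopes the value-0 rule for the maximum severity of any local reaction to an individual reaction where Table 3 needs all 3, and the continuous endpoints of Section 6.1.1.2 name systemic events instead of local reactions

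*SAP*

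**What the plan says.** **Maximum severity of any local reaction (SAP Section 3.1.1.2, variable 2).** Three bullets define the value.

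- *Missing*: "if values are missing for all days (Days 1-14) across all 3 local reactions".
- *0*: the bullet opens by requiring all reactions to be reported as *no*, or as a mix of *missing* and *no*, and closes "for all days (Days 1-14) for any individual local reaction".
- *Highest grade*: the bullet begins "Highest grade (maximum severity) within 14 days after vaccination, if the answer is not" *no*, and closes "for at least 1 day for at least 1 local reaction".

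Table 3 in Section 3.1.1.1 covers the presence of any local reaction over the same 14 days. It gives *No* only when the condition holds "on all 14 days for all 3 local reactions".

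The severity variable is used in Section 6.1.1.1: "Proportions of subjects reporting each and any local reactions after Vaccination 1 will be summarized by maximum severity level".

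**Supporting summaries (SAP Section 6.1.1.2).** The heading and lead sentence concern local reactions and refer to the definitions in Section 3.1.1. The three continuous endpoints listed are duration per systemic event, onset day per systemic event, and onset day of any systemic event. Section 6.1.2.2, which is about systemic events, lists the same three in identical words.

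**The concern.** A derivation should give each subject exactly one value. Here the scope of the 0 bullet differs from that of Table 3. In ordinary English, *any individual reaction* can mean at least one or every one. On the first meaning the 0 bullet and the highest-grade bullet both apply to a subject who has one reaction and lacks another. The 0 bullet is listed first, so a program that works down the list would return 0 for that subject.

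At stake is the any-local-reaction row of a primary tolerability summary, which would be too low if the 0 bullet were applied first. The programming rules are written separately, but Section 2 says they are based on this document, so the wording should be right here.

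In Section 6.1.1.2, a programmer who follows the bullets would tabulate systemic events twice. The itemised list would then omit the local-reaction duration and onset day that Sections 3.1.1.3 and 3.1.1.4 derive.

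**Working it through.** **Part 1: do the 0 rule and the highest-grade rule overlap?**

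Inputs: 3 local reactions and e-diary grades 0 to 3. The footnote to Table 4 says that Grade 4 is not reported from the e-diary. The rules are the bullets of variable 2.

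With a complete diary, each reaction has a 14-day maximum of 0, 1, 2 or 3.

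1. All patterns: 4^3 = 64. Patterns with at least one reaction present: 64 − 1 = 63.
2. Patterns with all three reactions present: 3^3 = 27.
3. Patterns with at least one present and at least one absent: 63 − 27 = 36.
4. *Any individual* read as at least one: all 36 meet both rules. Of these, 64 − 27 − 27 + 8 = 18 contain a Grade 3 (all patterns, less those with no 0, less those with no 3, plus those with neither).
5. *Any individual* read as every one: the 0 rule needs all three absent, so 0 of 63 overlap.

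Example for step 4: pain Grade 3, redness absent, swelling absent. Redness alone satisfies the 0 rule and pain alone satisfies the highest-grade rule, so the value is 0 or 3. Table 3 gives this subject *Yes*.

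Missing days do not change the conclusion. Add two states per reaction: missing on all days, and a mix of *no* and *missing*.

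- All patterns: 6^3 = 216.
- With a graded reaction: 216 − 3^3 = 189.
- Meeting both rules under at least one: 216 − 4^3 − 3^3 + 1 = 126.
- Meeting both rules under all 3, with *missing* and *no* pooled over the three reactions: 0, and no pattern is left without a value.

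The 64-pattern count is the more relevant one. Section 5.3.1.1 says the e-diary does not let a subject skip an item, so a missed day is missed for all three reactions. The larger count covers partly missing days, which Table 5 allows for ("or missing (for 1-2 of the reactions) on that specific day").

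One further looseness is that, in the highest-grade rule, an answer that is not *no* literally includes a missing day. A non-reactor with a missed day has no grade to take, and the 0 rule expressly provides for that mix, so no value changes.

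**Part 2: Section 6.1.1.2 against its own references**

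| Element of Section 6.1.1.2 | Concerns |
|---|---|
| Heading and lead sentence | Local reactions, as defined in Section 3.1.1 |
| Binary endpoint | Severe local reactions |
| Three continuous endpoints | Systemic events |
| The same three endpoints in Section 6.1.2.2 | Systemic events |

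The three bullets contradict the lead sentence above them and add nothing to Section 6.1.2.2. Also, Section 3.1.1.4 defines onset day for each reaction only, so once the bullets are corrected, onset of any local reaction will need a definition.

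**The case against.** The strongest reply is that the intent is plain. The 0 bullet opens by requiring all reactions to be *no*, the variable is by name a maximum, and Table 3 says all 3. Most of this stands, and all 3 is very probably what was meant. The opening words do not settle it, though, because variable 1 uses the same words for a single reaction. The *Missing* bullet helps only by parallel, since it defines *Missing* and not 0.

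A second reply is that a wrong coding would be noticed. That also stands. A graded reactor coded 0 would contradict Table 3 and the single-reaction rows. Where the reaction was severe, it would also contradict Table 5, which counts a severe report "on a specific day for any of the 3 local reactions", and the any-severe summary in Section 6.1.1.2. The bar charts in Section 6.1.1.1 plot each reaction separately and are unaffected. Section 5.1.2 makes all analyses descriptive, with no decision rules.

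On Section 6.1.1.2, the lead sentence is a general commitment to summarise the Section 3.1.1 endpoints, and Section 3.1.1 names duration and onset day among them. So a reader who infers that local-reaction duration and onset will never be summarised goes too far. What holds is that the itemised list contradicts that commitment.

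**Conclusion.** Both wording errors hold, and both are minor.

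The scope of the 0 bullet is ambiguous, and on one ordinary reading it conflicts with the highest-grade bullet in 36 of 63 non-zero patterns. That number counts logical patterns. The SAP gives no reaction rates, so it does not support a figure for the share of subjects affected. A reader might infer that the plan codes reactors as 0 or that the primary summary will be understated. The document does not support this: it would happen only if the phrase were taken as at least one and the 0 bullet were given precedence, and other outputs would reveal it.

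In Section 6.1.1.2 the three continuous endpoints are wrong as written, most likely carried over from Section 6.1.2.2. This affects supporting summaries only. The conclusion on both parts rests on the text alone and needs no numerical assumption.

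**What to change.** 1. In Section 3.1.1.2, variable 2, replace the 0 bullet with: *= 0 if 'no', or a mix of 'missing' and 'no', is reported on every day (Days 1-14) for all 3 local reactions.* Use the parallel wording for the maximum severity of any systemic event, since Section 3.1.2 handles systemic events in a similar way.
2. In the same edit, and for clarity only, make the highest-grade bullets of variables 1 and 2 depend on the reaction being reported as present on at least 1 day (for variable 2, at least 1 reaction).
3. In Section 6.1.1.2, replace *systemic event* with *local reaction* in the three continuous endpoints. Define onset of any local reaction as the earliest onset day across the 3 reactions.

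The cost is SAP wording only, with no change to data collection or design.

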3.1.1.3. Duration of Each Local Reaction

The duration of each local reaction will be calculated in days as (resolution date of reaction – start date of reaction + 1). Resolution of the event is the last day on which the event is recorded in the e-diary or the date the event ends if it is unresolved during the subject diary-recording period (end date collected on the case report form [CRF]), unless chronicity is established. However, if an event is ongoing at the time of a subsequent vaccination with RSV vaccine or its placebo control, the end date/day for the ongoing event will be the date/day that the next vaccination with RSV vaccine or its placebo control is administered, which will be used for the computation of the duration. If there is no known end date, the duration will be considered unknown and set to “missing.” Subjects with no reported reaction have no duration.

3.1.1.4. Onset Day of Each Local Reaction

The onset day of each local reaction will be derived. Onset day is defined as the first day of reporting any severity.

For the onset day of each local reaction, if a subject reports changes in severity of the local reaction, only the first day of reporting that specific local reaction will be counted.

3.1.1.5. Presence of Severe Local Reaction on Each Day

Presence (yes or no) of any severe local reaction on each of the 14 days (Day 1 through Day 14) follows the derivation as describe in Table 5.

Table 5. Derived Variables for Any Severe Local Reaction on Each Day

Variable	Yes (1)	No (0)	Missing (.)
Any severe local reaction on a specific day	Subject reports the severe reaction as “yes” on a specific day for any of the 3 local reactions.	Subject reports local reactions as any of the following: “no,” “mild,” or “moderate” (for 1-3 of the reactions) or missing (for 1-2 of the reactions) on that specific day.	Subject reports all 3 local reactions as “missing” on that specific day.

3.1.2. Systemic Events

Systemic events, including fever, fatigue, headache, vomiting, nausea, diarrhea, muscle pain, and joint pain, are reported via e-diary from Day 1 through Day 14 after Vaccination 1 [redacted] where Day 1 is the day of vaccination with RSV vaccine or placebo (Visit 1 for the sentinel/expanded cohort; [redacted]). The derivations below for systemic events will be handled similarly to the way local reactions are handled for presence, severity level, duration, onset day, and severe systemic events on each day.

1. Presence (yes or no) of each systemic event on any day (Day 1 through Day 14);

2. Presence (yes or no) of any systemic event on any day (Day 1 through Day 14);
3. Maximum severity of each systemic event on any day (Day 1 through Day 14);
4. Maximum severity of any systemic event on any day (Day 1 through Day 14);
5. Duration of each systemic event;
6. Onset day of each systemic event;
7. Presence (yes or no) of any severe systemic event on each of the 14 days.

The systemic events gradings are provided in Table 6.

Table 6. Grading Scale for Systemic Events

	Mild Grade 1	Moderate Grade 2	Severe Grade 3	Grade 4^a
Fatigue (= tiredness in diaries)	Does not interfere with activity	Some interference with activity	Prevents daily routine activity	Emergency room visit or hospitalization for severe fatigue
Headache	Does not interfere with activity	Some interference with activity	Prevents daily routine activity	Emergency room visit or hospitalization for severe headache
Vomiting	1 to 2 times in 24 hours	>2 times in 24 hours	Requires intravenous hydration	Emergency room visit or hospitalization for severe vomiting
Nausea	Does not interfere with activity	Some interference with activity	Prevents daily routine activity	Emergency room visit or hospitalization for severe nausea
Diarrhea	2 to 3 loose stools in 24 hours	4 to 5 loose stools in 24 hours	6 or more loose stools in 24 hours	Emergency room visit or hospitalization for severe diarrhea
Muscle pain	Does not interfere with activity	Some interference with activity	Prevents daily routine activity	Emergency room visit or hospitalization for severe muscle pain
Joint pain	Does not interfere with activity	Some interference with activity	Prevents daily routine activity	Emergency room visit or hospitalization for severe joint pain

- a. Grade 4 assessment should be made by the investigator using the AE severity grading scale. The assessment will be collected on the AE case report form, thus not included in the systemic event analysis.

Fever is defined as an oral temperature of $\geq 100.4^{\circ}\text{F}$ ($\geq 38.0^{\circ}\text{C}$). The highest temperature for each day will be recorded in the e-diary. Any temperature recorded as $< 95.0^{\circ}\text{F}$ (35.0°C) or $> 107.6^{\circ}\text{F}$ (42.0°C) will be treated as a data entry error and excluded from the analyses. For reporting purposes, fever will be analyzed using the following temperature ranges:

- 38.0°C to 38.4°C (100.4°F – 101.1°F)
- 38.5°C to 38.9°C (101.2°F – 102.0°F)
- 39.0°C to 40.0°C (102.1°F – 104.0°F)
- $> 40.0^{\circ}\text{C}$ ($> 104.0^{\circ}\text{C}$)

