6.1.2. Systemic Events

6.1.2.1. Primary Analysis

Endpoint: Proportions of subjects reporting prompted systemic events (fever, fatigue, headache, vomiting, nausea, diarrhea, muscle pain, and joint pain) within 14 days after vaccination.

- Analysis time points: Within 14 days after Vaccination 1.
- Analysis population: Safety population (sentinel cohort, expanded cohort, and combined sentinel and expanded cohorts).
- Analysis methodology: Descriptive summary statistics.
- Supporting objective: Primary objective.

Reporting Results:

Proportions of subjects reporting each and any systemic events after Vaccination 1 will be summarized by maximum severity level. Confirmed e-diary errors will be excluded from the analysis.

For each cohort, the percentage (%), the numerator (n) and denominator (N) used in the percentage calculation, and the corresponding 95% Clopper-Pearson CI will be presented for each vaccine group, by age stratum.

Figures: Bar charts with the proportions of subjects for each systemic event will be plotted for each vaccine group, by age stratum. The bar charts will be divided into severity subgroups to highlight the proportions of subjects by severity.

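### SAP 3.1.2: the Fahrenheit limits of fever bands 2 and 3 start 0.1°F below their Celsius limits, so 101.2°F and 102.1°F change band if converted to °C

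*SAP*

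**What the plan says.** SAP Section 3.1.2 sets the threshold ("Fever is defined as an oral temperature of" at least 100.4°F, or 38.0°C) and the source of the reading: "The highest temperature for each day will be recorded in the e-diary". It then states: "For reporting purposes, fever will be analyzed using the following temperature ranges". The first three bands are:

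- "38.0°C to 38.4°C (100.4°F – 101.1°F"
- "38.5°C to 38.9°C (101.2°F – 102.0°F"
- "39.0°C to 40.0°C (102.1°F – 104.0°F"

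The fourth band is above 40.0°C. Its bracketed equivalent is 104.0, printed with a Celsius unit where Fahrenheit is evidently meant.

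Fever is one of the listed systemic events, and Section 3.1 makes "Systemic events within 14 days after Vaccination 1" a primary endpoint. Section 6.1.2.1 adds: "Proportions of subjects reporting each and any systemic events after Vaccination 1 will be summarized by maximum severity level". Table 6, which grades the systemic events, has no row for fever, so these bands are its only gradation in the plan. The section does not say which unit governs, which unit the e-diary stores, or how a converted value is rounded.

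**The concern.** Each bracketed Fahrenheit range is offered as the equivalent of the Celsius range beside it. If the two differ, a temperature near a boundary can be banded one way by its Fahrenheit value and another way by its Celsius value. Two programmers could then both follow the section and produce different splits of fever by band. What is at stake is the distribution of fever cases across bands 1/2 and 2/3 in a primary safety table. The number of subjects with fever is not at stake.

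**Working it through.** **Inputs.** The thresholds and band limits come from SAP Section 3.1.2. Readings are assumed to have a resolution of 0.1 degree. The SAP does not state this, but the limits are printed to one decimal.

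**Formulas.** C = (F − 32) × 5/9 and F = C × 9/5 + 32.

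**The plan's own figures.** The outer limits convert exactly: 38.0 × 1.8 + 32 = 100.4°F and 40.0 × 1.8 + 32 = 104.0°F. The interior upper limits reproduce after rounding: 38.4°C = 101.12, or 101.1°F, and 38.9°C = 102.02, or 102.0°F. The interior lower limits do not:

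- 38.5 × 1.8 + 32 = 101.3°F; the SAP prints 101.2°F.
- 39.0 × 1.8 + 32 = 102.2°F; the SAP prints 102.1°F.

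Each printed lower limit is one 0.1°F step above the rounded upper limit of the band below. That is probably how it arose, though the SAP does not say so.

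**From °F to °C at the boundaries.**

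| Reading (°F) | Exact °C | Rounded °C | Band by °F limits | Band by rounded °C |
|---|---|---|---|---|
| 101.1 | 38.389 | 38.4 | 1 | 1 |
| 101.2 | 38.444 | 38.4 | 2 | 1 |
| 101.3 | 38.500 | 38.5 | 2 | 2 |
| 102.0 | 38.889 | 38.9 | 2 | 2 |
| 102.1 | 38.944 | 38.9 | 3 | 2 |
| 102.2 | 39.000 | 39.0 | 3 | 3 |
| 104.0 | 40.000 | 40.0 | 3 | 3 |
| 104.1 | 40.056 | 40.1 | 4 | 4 |

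Over every 0.1°F reading from 95.0 to 107.6°F, only 101.2 and 102.1 disagree. Left unrounded, their converted values (38.444 and 38.944) lie between the printed Celsius bands.

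**From °C to °F.** Every 0.1°C reading from 35.0 to 42.0°C, converted and rounded to 0.1°F, lands in the same band. For example, 38.5°C gives 101.3°F (band 2) and 39.0°C gives 102.2°F (band 3). The discrepancy therefore runs in one direction only.

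**Illustration of size.** The SAP gives no fever rate and no temperature distribution, so both inputs here are assumptions.

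- Suppose peak temperatures fall off exponentially above 100.4°F on the 0.1°F grid, with scale s between 0.6 and 1.6°F. The two readings lie 8 and 17 steps above 100.4°F. With q = exp(−0.1/s), their share of febrile subjects is (1 − q)(q^8 + q^17), or about 5% to 6%.
- Suppose also that 1% to 10% of subjects have fever. The planned total in Section 2.2 is 168 + 1014 = 1182. The expected number reclassified runs from 1182 × 0.01 × 0.05 = 0.6 to 1182 × 0.10 × 0.06 = 7.

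That range holds only if every reading is taken in °F and banded in °C.

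**The case against.** The strongest reply is that the discrepancy need never show in the results. At 0.1-degree resolution each printed scale is complete by itself, without gap or overlap. If all temperatures are recorded in one unit and banded in that unit, every fever falls in exactly one band. The reporting ranges put °C first with °F in brackets, which suggests that Celsius governs. SAP Section 2 also says that programming rules and mock-up tables are prepared separately, and those may settle conversion and rounding. All analyses are descriptive, and the SAP does not map these bands to mild, moderate or severe.

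Most of this stands, and it limits the consequence. It does not make the printed limits right. The order of units is not decisive either, because the fever definition and the data-entry error limits in the same section put °F first. Separate programming rules could fix the handling but would leave two wrong figures in the SAP.

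Three stronger readings are tempting and are not supported:

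- **The fever table as a whole depends on the unit.** This would need °F readings to be banded in °C, or a mix of recording units. The SAP states neither, and only two readings could differ.
- **Febrile subjects drop out of all four bands.** This happens only if an unrounded converted value is compared with limits printed to one decimal, which the SAP does not prescribe.
- **Group percentages shift materially.** One subject's share of a small group is the same for any misclassification and says nothing about how often this one would occur.

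**Conclusion.** Wrong as written, and minor. The Fahrenheit lower limits of bands 2 and 3 are each 0.1°F too low for their Celsius limits, the upper limits of bands 1 and 2 are correspondingly 0.1°F short, and the top band carries a wrong unit. The effect is confined to readings of exactly 101.2°F and 102.1°F, which move down one band when converted to °C and rounded. It also matters if recording units are mixed, since temperatures that agree to 0.1°C could then be banded differently. Fever yes/no and the band above 40.0°C are unaffected, because those limits convert exactly. The arithmetic rests on 0.1-degree readings. The count of affected subjects cannot be obtained from the SAP. It is probably small and could be zero.

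**What to change.** In SAP Section 3.1.2, correct the bracketed Fahrenheit limits to 100.4–101.2, 101.3–102.1, 102.2–104.0 and >104.0°F. Add one sentence: banding is done in °C, and °F entries are converted and rounded to 0.1°C first. For readings to 0.1°F, the same result follows from contiguous Celsius intervals applied to the converted value: ≥38.0 to <38.5, ≥38.5 to <39.0, ≥39.0 to ≤40.0, and >40.0°C.

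The cost is a line or two of text and a check of the banding code. Data collection and the fever definition stay as they are. The one drawback is that band labels would differ by 0.1°F from any earlier output that used the printed Fahrenheit limits.
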